## 11. PATIENT COMPLETION AND WITHDRAWAL

### 11.1. Patient Completion

Patients will be classed as having completed the trial once they have completed all required trial visits. See Section 11.2.1 for early discontinuations.

### 11.2. Patient Withdrawal

#### 11.2.1. Patient Withdrawal from Trial Treatment

A patient will be withdrawn from treatment for any of the following reasons:

Study Number: INVEX-CLIN-IIH-301 Protocol	Compound No.: Presendin
	Version: 3.0

- Withdrawal of consent to continue in the trial. The reason for this will be documented if provided
- The Investigator or Sponsor, for any reason, decides the patient should be withdrawn from the treatment
- Lack of compliance with the trial medication is classified as <75% or >125% of scheduled doses over the course of the trial, excluding supply issues
- Adverse events, which cannot be tolerated by the patient
- Pregnancy during the treatment period

Patients will be encouraged to continue in the trial to the end of the randomised treatment period even if they stop trial medication so that data can be collected for the Intention-To-Treat (ITT) population.

If a patient is withdrawn from treatment during the randomised treatment period, they will be encouraged to return for all trial visits up to visit 10. If a patient does not want to return then at a minimum they should be encouraged to attend for visit 11 procedures as a safety follow-up visit.

### **11.3. Treatment after the End of the Trial**

Patients will not be provided with trial medication following the end of the trial.

### **11.4. Screen and Baseline Failures**

Information will be collected on all patients who sign the Informed Consent Form (ICF).

## **12. ADVERSE EVENTS AND SERIOUS ADVERSE EVENTS**

### **12.1. Adverse Events**

An AE is any untoward medical occurrence in a patient or clinical investigation patient administered a pharmaceutical product and which does not necessarily have a causal relationship with this treatment. An AE can therefore be any unfavourable and unintended sign (including an abnormal laboratory finding), symptom, or disease temporally associated with the use of a medicinal (investigational) product, whether or not related to the medicinal (investigational) product.

#### **12.1.1. Causal Relationship**

Causal relationship assessment to drug treatments is required for purposes of reporting AEs. To promote consistency, the following guidelines should be taken into consideration

Study Number: INVEX-CLIN-IIH-301 Protocol	Compound No.: Presendin
	Version: 3.0

along with good clinical and scientific judgment when determining the relationship of drug treatments to an AE:

- Probable relationship: event occurs in a plausible time relationship to the medication administration and cannot be explained by concurrent disease or other drugs or chemicals; the response to the withdrawal of the drug should be clinically plausible
- Possible relationship: event occurs with a reasonable time sequence to the medication administration, but could also be explained by concurrent disease or other drugs or chemicals; information on the drug withdrawal may be lacking or unclear
- Unlikely relationship: event occurs with little temporal relationship to the medication administration and other factors such as drugs, chemicals or underlying disease provide plausible explanations
- Not related: event has no temporal relationship to the medication administration or there is a definite alternative aetiology

### 12.1.2. Severity Criteria

An assessment of severity grade will be made using the following categorical descriptors:

- Grade 1 means a relatively minor side effect
- Grade 2 means a moderate side-effect
- Grade 3 means a severe or medically significant but not immediately life-threatening side-effect
- Grade 4 means life-threatening consequences
- Grade 5 death related to AE

The exact definition of each number in the scale depends on the particular side effect according to Common Terminology Criteria for Adverse Events (CTCAE) v5.0 [CTCAE].

The Investigator should use clinical judgment in assessing the severity of events not directly experienced by the patient (e.g., laboratory abnormalities).

Adverse events occurring as a result of LP should be specifically recorded. Occurrence of post lumbar headache will be specifically reported.

### 12.1.3. Reporting Adverse Events

All AEs and special reporting situations, whether serious or non-serious, will be reported from the time a signed and dated informed consent form is obtained until completion of

Study Number: INVEX-CLIN-IIH-301 Protocol	Compound No.: Presendin
	Version: 3.0

the patient's final safety follow-up visit. The Sponsor will evaluate any safety information that is spontaneously reported by an Investigator beyond the time frame specified in the protocol. Adverse events reported after dosing will be classed as treatment emergent AEs.

All AEs, regardless of seriousness, severity, or presumed relationship to trial therapy, must be recorded using medical terminology in the source document and the eCRF. Whenever possible, diagnoses should be given when signs and symptoms are due to a common aetiology (e.g., cough, runny nose, sneezing, sore throat, and head congestion should be reported as "upper respiratory infection"). Investigators must record in the source documents and the eCRF their opinion concerning the relationship of the AE to trial therapy. All measures required for AE management must be recorded in the source document and reported according to Sponsor instructions.

The patient must be provided, on the first day of trial medication (Day 1), with a "patient card" indicating the following:

- Patient number
- Name of the investigational product
- Investigator's name and 24-hour contact information
- Statement that the patient is participating in a clinical trial

## **12.2. Serious Adverse Events**

An SAE is any untoward medical occurrence that at any dose:

- Results in death
- Is life-threatening
- Requires inpatient hospitalization or prolongation of existing hospitalization
- Results in persistent or significant disability/incapacity
- Is a congenital anomaly/birth defect

Medical and scientific judgement should be exercised in deciding whether reporting is appropriate in other situations, such as important medical events that may not reach the above definition but may jeopardise the patient or may require medical or surgical intervention to prevent one of the other outcomes listed in the above definition. These should also be considered serious. Examples of such events are invasive or malignant cancers, intensive treatment in an accident and emergency department or at home for allergic bronchospasm, blood dyscrasias or convulsions that do not result in hospitalisation, or development of drug dependency or drug abuse.

Study Number: INVEX-CLIN-IIH-301 Protocol	Compound No.: Presendin
	Version: 3.0

Deterioration of IIH necessitating CSF shunting or optic nerve sheath fenestration or dural venous sinus stenting will be recorded as an SAE and reported.

Deterioration of IIH necessitating hospital admission will be recorded as an SAE and reported.

Pre-defined exclusions:

- Hospitalisation for unrelated elective procedures
- Post LP headache

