### 3.3. Safety Endpoints

- Vital Signs
- Adverse events: Treatment-emergent adverse events (TEAEs), , serious adverse events (SAEs)
- Resting 12-lead electrocardiogram
- Routine laboratory assessments (haematology, biochemistry and urinalysis)

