### **12.2.2. Expected Adverse Events**

Perceived deterioration of IIH necessitating attendance or admission to hospital will not be reported as an SAE, but these events will be reported and recorded at follow-up. Non-protocol LPs will be reported at follow-up.

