### **12.2.3. Reporting Serious Adverse Events**

All SAEs occurring during clinical studies must be reported to the appropriate Sponsor designee (contract research organisation) within 24 hours of their knowledge of the event.

SAEs will be reported from the time a signed and dated informed consent form is obtained until completion of the patient's final safety follow-up visit.

Information regarding SAEs will be transmitted to the Sponsor's safety contact using the SAE Form, which must be completed and signed by the Investigator, and transmitted to the Sponsor's safety contact within 24 hours.

The contact details are:

The Sponsor assumes responsibility for appropriate reporting of SAEs or SUSARs to the regulatory authorities. The Investigator (or Sponsor where required) must report these events to the appropriate Independent Ethics Committee (IEC) that approved the protocol unless otherwise required and documented by the IEC.

Study Number: INVEX-CLIN-IIH-301 Protocol	Compound No.: Presendin
	Version: 3.0

An annual safety report will be submitted to the Institutional Review Board once a year via the Investigator.

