#### **13.3.4.1. Adverse Events**

All AEs, TEAEs, and SAEs will be coded using the MedDRA dictionary (the most recent version before starting the trial will be used).

An AE is defined as treatment-emergent if the first onset or worsening is after the first administration of trial medication.

The number and percentage of patients reporting TEAEs, grouped by MedDRA system organ class and preferred term will be tabulated by treatment group. Summaries will be presented for all TEAEs, TEAEs by severity and TEAEs by relationship to trial medication.

In the AE data listings, all AEs will be displayed. Adverse events that are not treatment-emergent will be flagged. The observation period in which an AE started will also be provided.

Non-protocol LPs, interventions for IIH, hospital admission for IIH exacerbation will be displayed by trial arm. Treatment failures will be displayed by trial arm.

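### In protocol v3.0, hospital admission for worsening IIH is an SAE under 12.2 but not under 12.2.2, so the same admission can be classed either way

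*Protocol*

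**What the plan says.** Section 12.2 (Serious Adverse Events) of protocol v3.0 lists the general criteria for seriousness, including "Requires inpatient hospitalization or prolongation of existing hospitalization". It then adds disease-specific rules. One makes worsening IIH that needs a CSF shunt, optic nerve sheath fenestration or a venous sinus stent an SAE. The next reads "Deterioration of IIH necessitating hospital admission will be recorded as an SAE and reported". The section closes with two pre-defined exclusions: "Hospitalisation for unrelated elective procedures" and headache after lumbar puncture.

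Section 12.2.2 (Expected Adverse Events) says "Perceived deterioration of IIH necessitating attendance or admission to hospital will not be reported as an SAE". Instead, "these events will be reported and recorded at follow-up".

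Section 12.2.3 sets the expedited route. "All SAEs occurring during clinical studies must be reported to the appropriate Sponsor designee", with a limit of 24 hours. Section 3.3 names SAEs among the safety endpoints.

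**The concern.** Both sections are mandatory instructions to sites, and they point in opposite directions for a patient admitted with worsening IIH. Nothing in the protocol says which takes precedence.

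Worsening IIH is the main disease risk here. Patients with papilloedema and visual field loss may spend 24 weeks on placebo, and the protocol cites the risk of visual loss as its reason for a short screening period. The sponsor also expects more use of ICP-lowering medication on placebo (13.3.1.1.1), so deterioration may differ between arms. If one site files an admission as an SAE and another follows 12.2.2, the SAE totals mix two definitions. Some admissions would also bypass the 24-hour route while the trial is running.

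**Working it through.** No sample size, power or error rate enters this point, so the check is a comparison of the text.

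| | 12.2 | 12.2.2 |
|---|---|---|
| Event | Deterioration of IIH with admission | Perceived deterioration of IIH with attendance or admission |
| SAE? | Yes | No |
| Route | 24 hours to the sponsor's designee (12.2.3) | "these events will be reported and recorded at follow-up" |
| SUSAR assessment | Possible, because the event is serious | Not triggered, because 12.2.1 requires seriousness |

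**Can the two rules be separated?** Three possible distinctions were tried.

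1. *The word 'perceived'.* The protocol does not define it. It does not say who does the perceiving, or how such a deterioration differs from any other once it has led to admission. It supplies no test that a site could apply.
2. *The heading 'Expected Adverse Events'.* Section 12.2.1 treats unexpectedness and seriousness as separate conditions for a SUSAR. Being expected does not make an event non-serious under the protocol's own terms.
3. *The exclusions in 12.2.* There are two, and IIH admission is neither. If 12.2.2 was meant as a third exclusion, 12.2 does not say so and states the opposite.

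**Which events are ambiguous?** An attendance without admission falls only under 12.2.2, apart from the general seriousness criteria. Deterioration needing one of the three named surgical procedures has its own SAE sentence in 12.2. The conflict therefore bites mainly on admissions for worsening IIH without one of those procedures.

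**What does 'follow-up' mean?** Section 12.2.2 does not define it. If it means the visit with that title, this is Visit 11, at week 29 in Table 1. If it means the next contact, it is sooner. Neither reading gives the 24-hour deadline.

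**Did revision resolve it?** No. The same two sentences stand in v1.0. Version 3.0 edited 12.2.3, adding the period over which SAEs are reported, and left the conflict in place.

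**How many events?** The protocol gives no expected rate of admission for IIH, so the number cannot be calculated.

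**The case against.** The best case against the point is that the information survives. Section 12.1.3 requires every adverse event to go into the eCRF whatever its seriousness. Section 13.3.4.1 adds: "Non-protocol LPs, interventions for IIH, hospital admission for IIH exacerbation will be displayed by trial arm". The later Other Safety Evaluations section repeats that display, and treatment failures are also shown by arm. A reader of the final report would see IIH admissions by arm whichever rule the sites had followed. This stands, and it limits the point. It does not restore 24-hour reporting or SUSAR assessment during the trial, and it does not make the SAE count consistent.

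A second argument is that 12.2.2 may be an intended exemption for disease-related events. That is possible, and the document does not say what was intended. An exemption would still have to agree with 12.2, which it does not.

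Several stronger readings are tempting but not supported:

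- *That arm differences would be hidden from the DSMC, or the SAE table made uninterpretable.* What the DSMC receives is set in its charter (14.6), which is not available, and the by-arm displays remain.
- *That the protocol's 5-10% expected to need more aggressive intervention (section 1.1, Visual Function) gives the number affected out of 240.* That figure is not an admission rate. If it means surgery, the named procedures already have their own SAE rule. If it includes medical rescue, admission does not follow.
- *That sites will count the event differently.* The text shows only that they can.
- *That the conflict is in the current protocol.* Only the closing appendices of v4.0 are at hand.

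**Conclusion.** The point holds as an internal contradiction in v3.0, present in the same words in v1.0. One admission for worsening IIH can be an SAE or not, depending on which section the site reads. The undefined word 'perceived' does not resolve it, and 12.2.2 conflicts with the protocol's own hospitalisation criterion.

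The effect is confined to two things: the SAE endpoint count, and whether the 24-hour route in 12.2.3 and SUSAR assessment apply. The admissions themselves stay in the eCRF and in the by-arm displays. The number affected is unknown.

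Two assumptions underlie this. The first is that no document outside the protocol, such as a safety reporting manual, already tells sites which rule to follow. The second is that v4.0 did not correct the text, which cannot be checked here. Within those limits it should be fixed, because a stated rule contradicts another on expedited safety reporting and the repair is small.

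**What to change.** Reconcile 12.2 and 12.2.2. The smallest edit that agrees with the seriousness definition in 12.2 is to delete 'or admission' from 12.2.2, leaving that section for attendance without admission.

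If the sponsor intends to exempt disease-related admissions, the exemption belongs among the pre-defined exclusions in 12.2. It needs a stated criterion in place of 'perceived', and the opposing sentence in 12.2 must be changed to match.

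Either way, check first whether v4.0 already resolves the conflict, and re-review any admissions already handled under 12.2.2.

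The cost is a one-sentence amendment, a notice to sites and, with the first option, a few more SAE forms. The exemption route needs slightly more drafting. Neither changes the design, the sample size or the efficacy analysis.

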### Intracranial pressure

IIH is a debilitating condition characterised by raised ICP, which is clinically measured by LP [Mollan, 2018]. The units for measurement of LP are cm CSF and cm H2O and these should be thought of as interchangeable and reflect the measurement of the height of the CSF column at LP. The measurement must be taken in the lateral decubitus position. Lumbar puncture is conducted to make a diagnosis of IIH. Lumbar puncture may be conducted in a clinical setting during the disease course to both monitor and treat the condition. Frequent therapeutic LPs are no longer recommended by the International IIH guidelines [Mollan, 2018]. This is because LP can be traumatic for patients and can occasionally cause significant complications (meningitis, spinal haematoma, pain) [Wright, 2012]. Hence, unnecessary LP's should be avoided. In some patients LP can alter other outcome measures, including measurements of papilloedema and headache [Yiangou, 2019]. Hence ideally, LP should be performed after these measures and symptoms have been assessed. Lumbar puncture can cause post-dural puncture headaches. The risk is 9-36% using a traumatic needle and 3-19% using an atraumatic needle [Wright, 2012]. Post-dural puncture headaches typically last less than a week but in some patients this can be longer [Yiangou, 2019]. Lumbar puncture pressure assessment of ICP reflects disease activity and is a useful and recognised outcome measure that has been utilised in other IIH trials [Markey 2020; Mollan 2021b].

Due to the invasive nature of LP, non-invasive measures of ICP are valuable. The majority of techniques historically evaluated as non-invasive surrogate measures of ICP lack sufficient quantification to be used clinically or in clinical trials. Optical coherence tomography (OCT) measures of the optic nerve have been shown to provide a useful surrogate measure to quantify changes in ICP [Vijay, 2020]. For example, at 12 months, Vijay *et al* showed that a change in optic nerve head height of 50  $\mu$  predicted a 5 cm CSF change in ICP [Vijay, 2020].

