#### 1.2. Risk/Benefit Assessment

Current treatments for IIH have limited efficacy and can cause disabling side effects. Acetazolamide, the most commonly used drug (off licence) has a high side effect profile (48% discontinued in a clinical trial due to intolerable side effects) [Ball, 2011]. Although IIH is a rare condition, incidence is rising with rising obesity trends. Improving IIH morbidity with new therapeutics is clearly an unmet need.

Safety data for Presendin (exenatide) is based on the IB (Pepton Inc.). Warnings include pancreatitis, hypoglycaemia when used in combination with a sulfonylurea, renal impairment, severe gastrointestinal disease and hypersensitivity.

Invex Therapeutics has considered these warnings and has defined eligibility criteria to ensure patient safety is paramount. As such patients with known contraindications to GLP-1 agonists, such as pancreatitis, ketoacidosis, severe gastrointestinal disease and renal impairment, will not be included. Additionally, diabetic patients receiving glucose lowering medication will be excluded.

An Independent Adjudication Committee (IAC), as described in Section 14.5, will assist the Investigators (when required) with the eligibility criteria of the patients to be enrolled,

Study Number: INVEX-CLIN-IIH-301	Compound No.: Presendin
Protocol	Version: 3.0

and also to determine treatment failures to ensure patient safety and the efficacy of the trial.

The most common adverse reactions experienced with exenatide are nausea, hypoglycaemia (only when used with other glucose lowering drugs, but these patients are excluded from the trial), vomiting, diarrhoea, feeling jittery, dizziness, headache and dyspepsia.

Patients receiving the active treatment during the randomised period may benefit by experiencing an improvement in their IIH symptoms, although this cannot be guaranteed.

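### Protocol v3.0 section 12.2 excludes post-LP headache from SAEs without any qualifier, against the section's own hospitalisation criterion, so a serious case falls outside 24-hour reporting

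*Protocol*

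**What the plan says.** Section 12.2 of protocol v3.0 lists the criteria that make any untoward medical occurrence an SAE. One is "Requires inpatient hospitalization or prolongation of existing hospitalization". The same section closes with a short list of pre-defined exclusions holding two items. The first is confined to a particular kind of admission: "Hospitalisation for unrelated elective procedures". The second is only "Post LP headache", with no condition attached. Section 12.2 of v1.0 has the same list.

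The reporting clock is in section 12.2.3: "All SAEs occurring during clinical studies must be reported to the appropriate Sponsor designee (contract research organisation) within 24 hours". Section 12.2.1 reserves SUSAR status for events that are serious as well as unexpected and thought to be related to the trial medication.

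Post-LP headache also appears in section 12.1.2, which says "Adverse events occurring as a result of LP should be specifically recorded" and "Occurrence of post lumbar headache will be specifically reported". Section 12.1.3 requires every AE to be entered in the eCRF whether or not it is serious.

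On frequency, the intracranial pressure part of section 1.1 says of post-dural puncture headache: "The risk is 9-36% using a traumatic needle and 3-19% using an atraumatic needle". It adds that these headaches usually last less than a week but can last longer.

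**The concern.** The definition and the exclusion give opposite answers for the same event. A patient admitted with a headache after the lumbar puncture meets the hospitalisation criterion, so the event is an SAE. It is also a post-LP headache, so it is not. Nothing in 12.2 says which rule prevails. Read literally, the exclusion wins, because it is a named exception to a general definition.

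The Week 24 puncture is a trial procedure and supplies the primary endpoint, whereas the diagnostic puncture is done by the clinical team before recruitment (section 6.3.1). Serious harm from a procedure that the protocol imposes should be classified by the same rules as any other serious harm. Causality matters too. Section 1.2 names headache among the common reactions to exenatide ("vomiting, diarrhoea, feeling jittery, dizziness, headache and dyspepsia"), and section 6.1.5 requires the puncture within 7 days of the last dose. A rule that settles seriousness by diagnosis also removes the event from SUSAR assessment, whatever its cause is later judged to be.

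**Working it through.** The core of the check is a comparison of texts. The arithmetic gives scale only.

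**Which headaches does the exclusion act on?**

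1. A post-LP headache that meets no criterion in 12.2 is not an SAE with or without the exclusion. The line has no effect on it.
2. A post-LP headache that meets a criterion (admission, prolonged stay, lasting disability, or the discretionary class of important medical events) is an SAE without the exclusion and not one with it.
3. The exclusion therefore changes classification only for headaches that meet, or could be judged to meet, a seriousness criterion.

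**What follows for those events?**

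- 12.2.3: the 24-hour duty is stated for SAEs, so it does not apply.
- 12.2.1: a SUSAR must be serious, so the event cannot qualify.
- SAE counts: the event is absent.
- 12.1.2 and 12.1.3: the event is still specifically reported and entered as an AE.
- 13.3.4.1: an onset after the first dose makes it treatment-emergent, so it appears in the TEAE tables by arm and by severity.

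**How many headaches?**

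Section 13.2.1.1 (ICP power) randomises 240 patients and assumes 40% to 50% of final punctures are missing. Its counts reproduce:

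- 50% missing: 240 × 0.50 = 120, or 60 per arm, as stated.
- 40% missing: 240 × 0.60 = 144, or 72 per arm, as stated.

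Expected headaches = number of punctures × risk:

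| Needle | Risk | Lowest | Highest |
|---|---|---|---|
| Atraumatic | 3% to 19% | 120 × 0.03 = 3.6 | 144 × 0.19 = 27.4 |
| Traumatic | 9% to 36% | 120 × 0.09 = 10.8 | 144 × 0.36 = 51.8 |

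Across both needle types, this is about 4 to 52 headaches.

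**How many of these would be serious?**

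The protocol gives no admission rate. With an assumed share of 2% to 10%:

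- Lowest: 3.6 × 0.02 = 0.07.
- Highest: 51.8 × 0.10 = 5.2.
- Highest with atraumatic needles only: 27.4 × 0.10 = 2.7.

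So about 0 to 5 events would be affected. Zero is a plausible outcome.

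**The case against.** The strongest reply is that the exclusion is deliberate and costs little. It sits under a heading for pre-defined exclusions, is repeated in v1.0, and concerns an expected effect of the procedure. Section 12.2 also has a discretionary class of important medical events, so a fixed rule spares sites a judgement about every headache that needs some intervention. The events are graded, recorded and tabulated by arm, so the safety signal survives. This much stands: data capture is intact, and the rule has some use for borderline cases. It does not explain why an admission, which needs no judgement, should be exempt, and no part of the protocol justifies that.

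A reader might infer more than the documents support:

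- *Serious LP complications in general go unreported as SAEs.* They do not. Only headache is on the list. Meningitis and spinal haematoma, both named in section 1.1, remain SAEs if they meet a criterion.
- *The 24-hour SAE route is the only prompt one, because Visit 11 (Day 204) is 35 days after Visit 10 (Day 169).* This is not established. Section 12.1.3 gives patients a card with the investigator's 24-hour contact and refers to sponsor instructions that are not shown. Nothing ties the entry of an AE to Visit 11.
- *Drug-related headache or IIH relapse will often be labelled as post-LP headache.* This is conjecture. Section 12.1.3 asks for a diagnosis where possible and for an opinion on causality.
- *Up to nine events could be affected.* That figure needs all 240 patients to have the puncture, every one at the 36% maximum, and 10% admitted: 240 × 0.36 × 0.10 = 8.6. The protocol itself plans for 120 to 144 punctures.

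**Conclusion.** Section 12.2 of protocol v3.0 contradicts itself: the unqualified exclusion removes from SAE status a post-LP headache that its own hospitalisation criterion makes serious. The loss is in SAE classification, the 24-hour duty, SUSAR assessment and SAE counts. It is not a loss of AE data, and it does not extend to other LP complications.

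The contradiction rests on the wording alone. Its size does not: about 4 to 52 headaches follow from the protocol's own figures and depend on needle type, while the 0 to 5 affected events depend on an assumed admission share of 2% to 10% that has no source in the documents.

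The conclusion can be shown only for v3.0 and v1.0. The v4.0 text available for this review is the end of its appendices, so whether its section 12.2 keeps the line is unknown.

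**What to change.** Reconcile sections 12.1.2, 12.2 and 12.2.3 in one of two ways:

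- delete post-LP headache from the pre-defined exclusions in 12.2; or
- keep it, limited to post-LP headaches that meet none of the seriousness criteria listed in that section.

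Under either wording, a serious post-LP headache is reported as an SAE under 12.2.3, and a non-serious one stays an AE reported under 12.1.2. The second option keeps the signal to sites that routine headaches need no SAE form.

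Check section 12.2 of v4.0 first, and make the change there if the line is still present. The edit is one line. Its running cost is a few more SAE reports. Treatment, visits and the efficacy analysis are unaffected.
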